**Nasal Iodophor Antiseptic vs Nasal Mupirocin Antibiotic in the Setting of Chlorhexidine
Bathing to Prevent Infections in Adult ICUS: A Randomized Clinical Trial
NCT#: 03140423**

8/14/2019

Mupirocin-Iodophor Swap Out Trial

Statistical Analysis Plan

[name]
August 14, 2019

Background

Universal decolonization of all adult ICU patients with daily chlorhexidine (CHG) baths is widely implemented as ICU standard of care with and without nasal mupirocin due to several trials including the REDUCE MRSA Trial. This 43-hospital trial showed a relative 37% reduction in ICU-associated methicillin resistant *S. aureus* (MRSA) clinical cultures and a relative 44% reduction in all-cause bloodstream infections.

Combined use of CHG with mupirocin is driven by the fact that *Staphylococcus aureus* is a common community and healthcare-associated pathogen responsible for disease in ICU settings. Nevertheless, the variability in mupirocin resistance in various geographic areas (near zero to >15%) has led intensivists to be circumspect in whether they implement universal CHG bathing alone or with universal mupirocin. While the majority of MRSA are still susceptible to mupirocin, the concern about whether mupirocin resistance will continue to rise has led to interest in finding alternative effective agents.

For this reason, the Mupirocin-Iodophor Swap Out Trial was undertaken as a cluster randomized non-inferiority trial in 137 HCA Healthcare hospitals with hospitals randomized to:

Arm 1: Mupirocin-CHG (Usual Care)

Hospitals will continue daily bathing with chlorhexidine plus twice daily intranasal application of mupirocin ointment upon admission to all ICUs and continuing for 5 days or until discharge from the ICU.

Arm 2: Iodophor-CHG

Hospitals will continue daily bathing with chlorhexidine, but switch from mupirocin to twice daily intranasal application of 10% povidone-iodine (iodophor).

Trial Outcomes

Trial outcomes are found in the below table.

Mupirocin-Iodophor Swap Out Trial Outcomes

Outcome	Metric
Primary Trial Outcome	ICU-attributable S. aureus clinical cultures (MRSA + MSSA)
Secondary Trial Outcomes (primary manuscript)	ICU-attributable MRSA clinical cultures ICU-attributable all-cause bloodstream infection
Other pre-specified secondary exploratory analyses for later manuscripts	Mupirocin and iodophor resistance in MRSA isolates

Analysis

The primary analysis will be an as-randomized proportional hazards model to evaluate for non-inferiority at a margin of 10% (difference in relative hazard). Model terms will include arm, period (baseline vs. intervention) and an arm by period interaction term to assess whether the difference in relative hazard between the baseline and intervention period differs significantly between the two arms. Clustering within hospital will be accounted for using shared frailties, i.e., a random intercept for each hospital, and, if it should become technologically feasible, an additional random intercept for each ICU within hospital and for repeated hospital stays for each person.

- Null hypothesis (H_0): the change in relative hazard of clinical culture of *S. aureus* in the Iodophor-CHG arm is higher than (inferior to) the change in the Mupirocin-CHG arm by more than 10%
- Alternative hypothesis (H_1): the change in relative hazard of clinical culture of *S. aureus* in the Iodophor-CHG arm is higher than (inferior to) the Mupirocin-CHG arm by 10% or less

Phase-in period data will not be included in the analysis.

To be explicit, the primary analysis will take the form of $\lambda_{ij}(t) = \lambda_0(t)e^{\beta_1 Arm_{ij} + \beta_2 Per_{ij} + \beta_3 Arm_{ij} * Per_{ij} + \gamma_i}$ where $\lambda_{ij}(t)$ is the time t of the *S. aureus* clinical culture for person j at hospital i . The baseline hazard function for time t , $\lambda_0(t)$, is shared by all people; γ_i is the frailty shared by patients at hospital i . The linear predictor in the exponent functions as in a linear model, where Arm_{ij} indicates the treatment arm of person j in hospital i is the iodophor arm, and Per_{ij} indicates that person j in hospital i was seen in the intervention period. Thus β_3 is the estimated differential effect of iodophor relative to mupirocin in the intervention period compared to baseline. While software is currently not able to include frailties for multiple visits per person or for multiple ICUs per hospital or for multiple periods per hospital on the scale of the data, we will include them if this should become possible by the time the trial is analyzed.

The primary outcome of the trial is ICU-attributable *S. aureus* clinical cultures (MRSA + MSSA) where ICU-attributable is defined as *S. aureus* cultures occurring in specimens collected from study cohort patients from the 3rd day of an ICU stay through 2 days after ICU discharge. This outcome will be assessed using an as-randomized unadjusted proportional hazards model as described above with two-sided significance set at alpha = 0.05, consistent with FDA standards of non-inferiority (<https://www.fda.gov/regulatory-information/search-fda-guidance-documents/non-inferiority-clinical-trials>). The pre-specified non-inferiority margin, we repeat, is 10%.

There is reason to suspect that nasal iodophor may be inferior to mupirocin due to FDA clearance based upon suppression versus cidal kill for *S. aureus*, which is the reason for the non-inferiority trial. However, conversely, if iodophor is found to be non-inferior, we are declaring the a priori intent to assess for superiority because of evidence of mupirocin-resistant *S. aureus* strains where none is expected to exist for iodophor. For this reason, if iodophor is found to be non-inferior in the primary outcome of the trial, we will also report the pre-specified assessment of superiority which is already performed in the primary analysis.

Secondary non-inferiority outcomes include 1) ICU-attributable MRSA clinical cultures and 2) ICU-attributable all-cause bloodstream infection. These will be assessed using an as-randomized unadjusted proportional hazards model as described above. We will use two-sided significance tests set at $\alpha = 0.05$ for each outcome to determine possible inferiority with greatest possible sensitivity, again with a non-inferiority margin of 10%. Due to the above antibiotic-resistance rationale to suspect possible superiority, if non-inferiority is met for these secondary outcomes, we will perform a pre-specified assessment of superiority at a two-tailed significance set at $\alpha = 0.025$, which accounts for the multiple comparisons of two outcomes. To be clear, the non-inferiority tests are not adjusted for multiple testing, while the superiority tests, if they are performed, will be adjusted for multiple testing, for conservatism.

Additional analyses will include as-treated and adjusted models, which will be reported as point estimates with confidence intervals without p-values. The reason for including these analyses is to provide additional information related to the trial outcomes for reader assessment of potential confounders. The reason to not include them in a formal multiple comparisons adjustment is because these analyses are non-independent evaluations related to the as-randomized unadjusted analyses.

Power and Sample Size

While 140 HCA hospitals are eligible for recruitment, we have HCA corporate commitment to assure the participation of at least 120 hospitals. Power was assessed using simulation methods. We simulated hospitals using information from HCA regarding ICU size and from a prior trial (REDUCE MRSA Trial) regarding likely rates of *S. aureus* in the baseline period. With 120 hospitals, we will have 82% power to detect non-inferiority within a hazard ratio of 1.1, based upon 2014 HCA ICU-attributable *S. aureus* clinical cultures of 4.8 cases per 1,000 ICU-days. While the intent is to confirm non-inferiority, we assume that iodophor will eradicate 5% more *S. aureus* than mupirocin due to existing mupirocin resistance. We estimate that total ICU patients in the intervention period will be ~171,500 patients who stay >2 ICU days.

NOTE: This statistical analytic plan was updated post-completion of the trial, but prior to accessing the trial dataset for cleaning or analysis. It was updated in response to the Harrington et al. (NEJM 2019;381:285-6) publication on “New Guidelines for Statistical Reporting in the *Journal*.”

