Table 1. Mupirocin-Iodophor Swap Out Trial Design Characteristics and Outcomes

[figure not shown]
Study Design	Cluster-randomized non-inferiority clinical trial
Unit of Randomization	Hospitals (all ICUs in a hospital will be assigned to the same regimen*)
Study Population	Adult ICU patients in participating HCA hospitals
Inclusion Criteria	Hospitals with at least 1 adult ICU, stable infection prevention initiatives and products during baseline period, agreement to refrain from new initiatives conflicting with the trial
Exclusion Criteria	ICUs with mean length-of-stay of less than 2 days. HCA hospitals having an electronic health record other than MEDITECH.
Group Assignments Arm 1 (N=60 hospitals) Arm 2 (N=60 hospitals)	Routine care: ICU decolonization with daily CHG baths and mupirocin for 5 days, twice daily Intervention: ICU decolonization with daily CHG baths and iodophor for 5 days, twice daily
Study Period	24-Month Baseline Period (Retrospective Data): May 2015 – Apr 2017 4-Month Training and Phase In Period: May – Oct 2017 (not included in analysis) 18-Month Intervention Period: Nov 2017 – Apr 2019
Primary Outcome	ICU-attributable S. aureus clinical cultures (MRSA + MSSA)
Secondary Outcomes	ICU attributable MRSA clinical cultures; ICU-attributable all-cause bloodstream infection;

* patient-level data will be analyzed by hospital

This trial will be registered with Clinicaltrials.gov, following approval by the Harvard Pilgrim Health Care Institutional Review Board, but prior to intervention launch.

Randomization will occur on the hospital level. All adult ICUs in a given hospital will be assigned to the same regimen (Figure 1).

Figure 1: Study Arms of Mupirocin-Iodophor Swap Out Trial

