1.2.12 Data Collection

Descriptive data, outcome data and variables for addressing confounding will be derived from microbiology, census, pharmacy, and claims data from participating hospitals. The following data elements will be collected (Table 6) using encrypted study IDs.

Table 6. Data Elements

Source Data	Result Types	Elements
Microbiology: Finalized Results	All positive and negative cultures	Pathogen name (if culture is positive), patient identifier, date of collection, body site of collection, antimicrobial susceptibility
Census Data	Line item per admission	Patient identifier, hospital admission date, hospital discharge date, ICU vs. non-ICU charge code by calendar date, age in years, gender
Claims Data	Line item per admission	For case mix adjustment: Diagnosis codes (ICD9-ICD10) Procedure codes (ICD9/ICD10/CPT codes)
Pharmacy	Mupirocin and iodophor dispensing	Patient identifier, date range dispensed, ICU location

Nursing Queries	Bathing responses	Data on whether a bath was given, and if yes, with a CHG or non-CHG bathing soap product.
-----------------	-------------------	---

We will use claims data to collect diagnostic and procedure codes that will be used for case mix adjustment for both hospital-wide, ICU-specific, and post-ICU outcomes. Case mix will be assessed using a comorbidity score (e.g. Elixhauser score) as well as evaluating the individual components of that score (e.g. diabetes, renal disease) and evidence of major surgery.

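### Does the primary model, written with one event time and one period per person, put patients seen in both periods into the wrong period?

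*SAP*

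**What the plan says.** The SAP (Analysis) and Protocol 1.2.13 give the same proportional hazards formula: arm, period, their interaction and a hospital frailty. It carries two subscripts, hospital i and person j. The left-hand side "is the time t of the *S. aureus* clinical culture for person j at hospital i", and the period covariate "indicates that person j in hospital i was seen in the intervention period".

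The surrounding text is about stays. If software allows, the model is to gain "an additional random intercept for each ICU within hospital and for repeated hospital stays for each person". The outcome counts "cultures occurring in specimens collected from study cohort patients from the 3rd day of an ICU stay through 2 days after ICU discharge". Protocol 1.2.12 describes census and claims data as "Line item per admission", with "ICU vs. non-ICU charge code by calendar date". Protocol Table 1 sets the periods by calendar: a "24-Month Baseline Period (Retrospective Data"), May 2015 to April 2017, and an 18-month intervention period, November 2017 to April 2019. The phase-in months between them are left out of the analysis.

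The text available for review does not say in so many words whether an analysis row is a person, an admission or an ICU stay. One part of the protocol, between sections 1.2.2 and 1.2.4, was not available, so a definition there cannot be ruled out.

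**The concern.** A formula introduced as the explicit form of the primary analysis ought to settle how each record is coded. This one gives person j a single time and a single period value, although some people will have several stays over the 42 months analysed (24 + 18).

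Take a patient at an iodophor hospital with one stay in 2016 and another in 2018. The literal definition sets the period to intervention. If the single event time came from the 2016 stay, experience under mupirocin would be analysed as iodophor intervention experience. In a superiority trial such dilution is usually conservative. Here it is not: if iodophor were truly worse by the full margin, dilution moves the estimate toward 1 and makes a false claim of non-inferiority more likely. The null and alternative hypotheses are stated on exactly this arm-by-period contrast, so the point deserved a check.

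**Working it through.** **Which coding does the text support?**

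1. A random intercept for a person's repeated stays can be estimated only if that person contributes more than one row. The plan wants this term and holds it back only for software reasons. The intended rows are therefore stays or visits.
2. Period is a calendar window, and phase-in data are dropped by date. A dated stay falls in one period (stays that cross a boundary aside).
3. With one row per stay, the 2016 stay has period 0 and the 2018 stay has period 1. No misplacement arises.
4. The remaining details follow from the outcome definition. The window opens on ICU day 3, the power section counts patients staying more than 2 ICU days, and follow-up ends 2 days after ICU discharge. In a time-to-event model with one event per row, the first qualifying culture sets the time.

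**How large would the harm be under the literal reading?**

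Inputs from the documents: margin 1.10; two-sided alpha 0.05; 82% power with 120 hospitals; assumed 5% advantage for iodophor, taken as HR 0.95; 24 and 18 months. Assumptions: variance driven by event counts; event time taken from the first stay; and w, the share of intervention-period patients with an earlier baseline stay in the same hospital, set at 2%, 5% and 10% because the documents do not give it.

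*Standard error implied by the plan's power.* SE = (ln 1.10 − ln 0.95)/(1.960 + 0.915) = 0.1466/2.875 = 0.0510.

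The 82% came from simulation and cannot be reproduced strictly, because days at risk per patient and hospital-by-period variance are not given. As a plausibility check, take Var = 4/E + 4/(E × 24/18) = 7/E, with E intervention-period events. About 3.27 days at risk per patient give E = 171,500 × 3.27 × 4.8/1,000 ≈ 2,692 and SE = √(7/2,692) = 0.0510. So 82% is compatible with the inputs, but neither confirmed nor refuted.

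*Literal period code, time from the first stay.*
- Analysed HR = w + (1 − w) × HR.
- Variance multiplier = [1 + 0.75/(1 − 0.75w)]/1.75.
- P(non-inferiority) = Φ[(ln 1.10 − ln HR analysed)/SE − 1.96].

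| w | SE | Analysed HR if true HR is 1.10 | False non-inferiority | Power at HR 0.95, 120 hospitals |
|---|---|---|---|---|
| 0 | 0.0510 | 1.100 | 2.5% | 82% |
| 2% | 0.0512 | 1.098 | 2.7% | 81% |
| 5% | 0.0514 | 1.095 | 3.1% | 80% |
| 10% | 0.0519 | 1.090 | 3.7% | 78% |

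*At the 137 hospitals reported in the SAP Background.* SE = 0.0510 × √(120/137) = 0.0477. Power is then 87% with no overlap, and 86%, 85% and 83% for w = 2%, 5% and 10%. The error is 2.7%, 3.1% and 3.8%.

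*Each person placed by the first stay instead.* The variance multiplier is [1/(1 − w) + 0.75]/1.75. There is no dilution, the error stays at 2.5%, and power at 120 hospitals is 82%, 81% and 80%.

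**The case for a change.** The strongest reply is that a prespecified formula should not depend on a sensible reader. A person frailty handles correlation between stays; it does not define the period code, time zero, censoring or which culture counts. The SAP was revised before anyone opened the trial dataset, so one more subscript would have cost nothing, and the error under the literal reading runs in the anti-conservative direction.

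The description is right: the subscript is absent, the row is not named, and a hazard is called a time. The consequence is not established. The inflation needs two choices together, a period code fixed for the whole person and an event time from the baseline stay. The second appears nowhere in the documents, and the first makes the planned repeated-stay term meaningless.

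A related doubt is whether the power calculation's "clinical cultures of 4.8 cases per 1,000 ICU-days" were counted by the rule the model uses. On event-driven variance, power at 120 hospitals would fall below 80% if more than about 5% of those cases did not qualify; at 137 hospitals the limit is about 17%. But the SAP describes that rate with the same ICU-attributable term that it defines for the outcome, and nothing in either document points to a different count.

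Stay-level rows do leave correlation between one person's stays unmodelled until the extra frailty can be fitted. The plan says so openly, as a limit of software at this scale of data.

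**Conclusion.** The concern does not call for a change. The explicit formula is loosely indexed, but the text around it, the calendar definition of the periods and the ICU-stay outcome window lead an analyst to one row per stay, dated to its own period. Under that coding the test has its nominal one-sided 2.5% error.

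Under the least favourable reading examined, the error would be 2.7% to 3.7% for an assumed overlap of 2% to 10%, and power at the 137 hospitals reported would stay at 83% or more. Those figures rest on an overlap that the documents do not give, on event-driven variance, on 82% power having been computed at HR 0.95, and on a choice of event time that the plan does not make. The missing stay subscript and the hazard described as a time are clerical; neither alters the primary result.

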1.2.5 Randomization

Randomization will occur during Spring 2017 and participating hospitals will be notified. This will be done because of the requisite 3-5 month period to submit and schedule the approval of intervention protocols by relevant hospital committees which often meet monthly or quarterly. As per routine policy in all hospitals, no training or implementation activities may occur prior to obtaining requisite hospital committee approvals. This will allow approval to occur and appropriate training of staff to occur prior to the phase in period which will involve acquisition and introduction of intervention product.

[figure not shown]
While this study is one of the largest cluster-randomized trials of hospitals, simple randomization of 120 hospitals will not ensure balance of key variables by chance alone, and without care could even result in very unequal numbers of hospitals in each arm. Achieving balance on key features of the randomization units (in this case, hospitals) is a critical task in cluster-randomized trials, but little literature on it exists. Unlike individually-randomized trials, information about the clusters is often known in advance, but the number of clusters to be randomized can be relatively small. The existence of a priori data can mitigate the small numbers and help to obtain adequate balance through stratification or other methods. One attractive approach is to establish tuplets—matched sets (pairs, for a two-arm trial) – in which one member of each tuplet is

assigned to each arm. Schemes for constructing tuples need not be guided by theory. A formal approach would be to calculate the Mahalanobis distance between hospitals across all key variables and choose the set of tuples with the minimum average distance. In this approach, we could standardize the variables, and then multiply by values calibrated to reflect any difference in the importance of balancing them. Other approaches are more ad hoc, such as prioritizing broad classes of balance on a key variable and making pairs within these strata based on lower-priority variables. However, there is no “best” method of tuple construction, only sets that come closer to meeting the varied needs of each trial.

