As a final note, we could consider the relative costs and benefits of strata of four, rather than tuples, which are strata of two. There are sound statistical reasons to expect power to be slightly better with strata of four, although there is some debate on this point. However, the balance between the arms may be worse. The balance is of central importance, since balance ensures that the observed effect is not confounded—confounding requires that the confounder be out of balance between the arms. We will examine whether the

gain in power is strong enough, and the loss of balance slight enough, to pursue strata of four in place of triplets.

We will focus on balancing the baseline outcome values in participating hospitals, baseline adherence to the HCA guidance for universal decolonization with chlorhexidine and mupirocin, measures of case severity index, and ICU patient day volume. We will additionally consider accounting for demographics, and ICU length of stay.

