1.2.13 Statistical Analysis and Power

The primary analysis will be an as-randomized proportional hazards model to evaluate for noninferiority at a margin of 10% (difference in relative hazard). Model terms will include arm, period (baseline vs. intervention) and an arm by period interaction term to assess whether the difference in relative hazard between the baseline and intervention period differs significantly between the two arms. Clustering within hospital will be accounted for using shared frailties, i.e., a random intercept for each hospital, and, if it should become technologically feasible, an additional random intercept for each ICU within hospital and for repeated hospital stays for each person.

- Null hypothesis (H_0): the change in relative hazard of clinical culture of *S. aureus* in the Iodophor-CHG arm is higher than (inferior to) the change in the Mupirocin-CHG arm by more than 10%
- Alternative hypothesis (H_1): the change in relative hazard of clinical culture of *S. aureus* in the Iodophor-CHG arm is higher than (inferior to) the Mupirocin-CHG arm by 10% or less

Phase-in period data will not be included in the analysis.

To be explicit, the primary analysis will take the form of $\lambda_{ij}(t) = \lambda_0(t)e^{\beta_1 Arm_{ij} + \beta_2 Per_{ij} + \beta_3 Arm_{ij} * Per_{ij} + \gamma_i}$ where $\lambda_{ij}(t)$ is the time t of the *S. aureus* clinical culture for person j at hospital i . The baseline hazard function for time t , $\lambda_0(t)$, is shared by all people; γ_i is the frailty shared by patients at hospital i . The linear predictor in the exponent functions as in a linear model, where Arm_{ij} indicates the treatment arm of person j in hospital i is the iodophor arm, and Per_{ij} indicates that person j in hospital i was seen in the intervention period. Thus β_3 is the estimated differential effect of iodophor relative to mupirocin in the intervention period compared to baseline. While software is currently not able to include frailties for multiple visits per person or for multiple ICUs per hospital on the scale of the data, we will include them if this should become possible by the time the trial is analyzed.

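### The limit for β3 rests on a hospital frailty that is constant over time; variation between hospitals in their change over time is left to software, with no fallback variance

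*SAP*

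**What the plan says.** The SAP (Analysis) and Protocol 1.2.13 write the same model: arm, period, arm × period, and one frailty γ_i indexed by hospital only. The commitment reads "Clustering within hospital will be accounted for using shared frailties, i.e., a random intercept for each hospital". Intercepts for ICUs and for repeat stays are conditional on feasibility.

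The two documents then differ on what software cannot yet handle. The protocol lists "frailties for multiple visits per person or for multiple ICUs per hospital on the scale of the data". The SAP adds a third item and treats it in the same conditional way: "or for multiple periods per hospital on the scale of the data, we will include them if this should become possible".

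The primary analysis carries no covariates: "This outcome will be assessed using an as-randomized unadjusted proportional hazards model as described above". Both secondary outcomes use the same model. The additional analyses are as-treated and adjusted models; neither changes how the variance of β3 is obtained. No robust variance, jackknife, bootstrap, permutation test or cluster-level analysis is named in either document.

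**The concern.** β3 compares within-hospital changes between the arms. An intercept that is equal in both periods drops out of each hospital's change almost entirely, so it cannot represent hospitals whose rates move by different amounts between a 24-month baseline and an 18-month intervention period. Changes in case mix, culturing practice, adherence or local outbreaks would all produce such movement.

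If it exists and is not modelled, β3 stays centred where it should be but its standard error is too small. In this trial that error favours the new product. Non-inferiority is declared when the upper 95% limit lies below 1.10, and superiority is then read from the same interval. More patients per hospital do not reduce the missing component; only the number of hospitals does.

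**Working it through.** **Inputs from the documents.** Margin HR 1.10, two-sided α 0.05 (one-sided 0.025), 82% power with 120 hospitals, iodophor assumed 5% better (read as HR 0.95), 4.8 events per 1,000 ICU-days, about 171,500 intervention patients (SAP, Analysis and Power and Sample Size); 60 hospitals per arm, 24 and 18 months (Protocol Table 1).

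**Assumptions.** ω, hospital-size CV 0.6 and between-hospital SD 0.4 are not in the documents.

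**Step 1: the standard error implied by the stated power.** The 82% cannot be reproduced directly, because ICU-days per patient and the simulation's variance components are not given. Solved backwards:

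- SE = (ln 1.10 − ln 0.95)/(1.96 + 0.915) = 0.1466/2.875 = 0.0510.
- With E intervention events and 4E/3 baseline events, split equally by arm, Var(β3) = 2(2/E) + 2(1.5/E) = 7/E. So E = 7/0.0510² ≈ 2,690.
- At 4.8 per 1,000 this is 2,690/(0.0048 × 171,500) ≈ 3.27 at-risk days per patient.

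**Step 2: add drift.** Let ω be the SD of log hazard per hospital-period. A hospital's change then has variance 2ω² (SD 0.14 when ω = 0.10). Over two arms of 60 hospitals:

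- SE_true² = 0.0510² + 4ω²(1 + CV²)/60.
- One-sided error = 1 − Φ(1.96 × 0.0510/SE_true).

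Example, ω = 0.10 and CV = 0: SE_true² = 0.002601 + 0.000667, SE_true = 0.0572, ratio 1.12, error 4.0%.

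**Step 3: simulation.** Hospital-period counts, shared gamma-frailty Poisson likelihood, true HR 1.10, 120 hospitals, CV 0.6, 10,000 replicates per cell (Monte Carlo SE 0.15–0.3 points). Matching was either by Mahalanobis pairs on baseline rate, volume and two unrelated variables, or by pairs on baseline rate alone.

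False non-inferiority, % (nominal 2.5):

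| ω | Formula, equal sizes | Formula, CV 0.6 | Simulated, unmatched | Simulated, Mahalanobis pairs | Simulated, pairs on baseline rate |
|---|---|---|---|---|---|
| 0 | 2.5 | 2.5 | 2.2 | 2.1 | 2.2 |
| 0.05 | 2.9 | 3.0 | 3.1 | 2.7 | 2.7 |
| 0.10 | 4.0 | 4.6 | 5.2 | 4.4 | 4.2 |
| 0.15 | 5.9 | 7.1 | 8.0 | 7.2 | 6.8 |
| 0.20 | 8.4 | 10.3 | 11.4 | 10.7 | 9.6 |

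- Independent reruns with pairing on baseline rate, from equal sizes to CV 0.6, gave 2.2–2.7% at ω = 0.05 and 3.2–4.0% at 0.10.
- With 136 matched hospitals (68 pairs, standing in for the 137 in SAP, Background) and events scaled up, the errors over the same ω values are 2.1, 2.6, 4.7, 6.7 and 10.3%. Extra hospitals shrink both variance components, so the ratio does not improve.
- With half the events, as might apply to MRSA, they are 1.9, 2.1, 3.0, 4.5 and 6.4%.
- No bloodstream-infection rate is given, so no figure is offered for that outcome.

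**Step 4: the Cox frailty model itself.** About 400,000 simulated patients, matched, 600 replicates per ω (Monte Carlo SE 0.6–1.3 points):

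| ω | Mean model SE | True SD of β3 | Error, model SE | 
|---|---|---|---|
| 0 | 0.051 | 0.049 | 3.0% |
| 0.05 | 0.051 | 0.053 | 2.7% |
| 0.10 | 0.051 | 0.056 | 3.5% |
| 0.20 | 0.051 | 0.083 | 10.8% |

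The model SE does not respond to drift at all. Jackknife error in these runs was 1.5–2.5%.

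**Step 5: does data scale prevent the fit?** The primary model is unadjusted, so every committed term is constant within a hospital-period. With time in days and Breslow ties, patient rows collapse without loss to events and numbers at risk by hospital, period and day. In the simulation 400,172 patients became 5,166 cells, and the hospital-by-period frailty fit took under 2 seconds. A separate check on 35,002 rows with hospital indicators gave identical β3 (0.0652785) and SE (0.1914856) from the patient-level and collapsed data.

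**Step 6: a rough scale for ω.** Suppose log hazard moves in proportion to adherence, using the 37% MRSA effect in Protocol 1.1. A between-hospital SD of 15 points in adherence change gives 0.462 × 0.15/√2 = 0.049; 30 points gives 0.098.

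**The case against.** **The SAP already promises the term if it can be fitted.** If fitting is easy, the condition is met and the term is required. But the SAP states that it is not feasible at this scale, and an analyst following that statement would report the constant-frailty interval. The variance behind the primary conclusion should not depend on a later judgement about software.

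**Drift may be small.** On the only scale the documents support, ω = 0.10 needs a 30-point SD in adherence change. Training in both arms, adherence tracking, an 85% goal and the bar on conflicting initiatives all argue against that. This stands: adherence drift alone may be harmless. Drift from case mix, culturing and outbreaks would add to it and cannot be sized from the documents.

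**Matching.** The protocol plans to balance hospitals ("We will focus on balancing the baseline outcome values in participating hospitals") and also considers adherence and case severity, which could predict drift; the simulation used two unrelated variables in their place. The protocol fixes no pairing scheme, so the matched results are themselves an assumption. Matching lowers the error, and at small ω it can keep it at or below nominal. It did not remove the inflation from 0.10 upwards in the count simulations with CV 0.6.

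**The Cox runs show no clear excess at 0.10.** True: 3.5% with 600 replicates cannot be told apart from 2.5%. The case at 0.10 rests on the larger count simulations and the formula, so 0.10 is where inflation starts. At 0.20 all methods agree.

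**Conclusion.** The concern holds. The plan commits to a variance for β3 that ignores differences between hospitals in their change over time, names that source of variation, and gives no rule if it cannot be modelled. With no drift nothing is wrong. In the matched simulations the one-sided error is 2.1–2.7% at ω = 0.05, roughly 3–4.7% at 0.10, and about 6.4–10.8% at 0.20, where the low end is the half-events case. The ratio of true to model SE does not depend on the true hazard ratio, so by the same formula the superiority test is exposed too; no separate simulation of it was run.

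These figures rest on an unknown ω, on assumed hospital sizes, and on the event count implied by reading the stated power at HR 0.95. They do not show the 82% power to be wrong: the power text describes its inputs only as "We simulated hospitals using information from HCA regarding ICU size and from a prior trial (REDUCE MRSA Trial" and similar, without saying whether hospital-by-period variance was included. This should be fixed; confidence in its practical size is medium.

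**What to change.** For the primary and both secondary outcomes, replace the conditional wording with one pre-specified variance for β3:

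- **Primary.** Keep the Cox frailty point estimate. Take its variance from a hospital-clustered sandwich or a leave-one-hospital-out jackknife, with a t reference on hospitals minus 2 degrees of freedom. This also covers ICUs within hospital and repeat stays, except for patients seen at more than one hospital.
- **Sensitivity.** Fit hospital and hospital-by-period random effects to data collapsed to hospital, period and day, or a Poisson model on hospital-period counts.

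The cost is SAP wording and a short program; the 120-hospital jackknife ran in under 1 second. In the count simulation with 120 matched hospitals the robust variance held the error at 2.2–2.4% for every ω from 0 to 0.20. With no drift, the SE is 0.050 (robust) or 0.051 (jackknife) against 0.0505 from the model, and the critical value is 1.98 instead of 1.96.

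There are two downsides. The robust variance is slightly conservative when matching works well. If drift is real, intervals widen: should the 82% have assumed none, power by formula, Φ(0.1466/SE_true − 1.96), at ω = 0.05, 0.10 and 0.15 is 80, 73 and 63% with equal hospital sizes, and 79, 70 and 58% with CV 0.6. If the original simulation already included this variance, that loss is already counted.
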